6.1 Study Assessments

6.1.1 Efficacy Assessments

Primary Endpoint: The response rate of R+P will be evaluated using RECIST 1.1 as well as iRECIST. Disease status will be measured by CT scan at baseline and then once every two cycles and as clinically indicated. Radiographic response per RECIST v.1.1 and iRECIST criteria (Appendices 1 and 2) will be determined by comparison to the tumor measurement obtained at baseline. Tumor progression will be determined by comparison to the smallest tumor measurement at either baseline or after initiation of therapy. The baseline disease assessment must be recorded and measured within 28 days prior to treatment start. During the treatment period, disease assessments will be performed every 6 weeks, i.e. once every two cycles, and as clinically indicated.

Secondary Endpoints: Safety and tolerability will be assessed with adverse event (AE) assessments at each study visit. CTCAE v5.0 will be used for adverse event grading. Attributions of causality will be assessed by the primary treating physician. Clinical benefit rate (stable disease + responses) will be assessed using the same criteria as response rate and on the same schedule. Survival will be measured from the date of study registration to the date of event (i.e., death or progressive disease) or the date of last follow-up if no event has occurred at their last evaluation.

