9. STATISTICAL CONSIDERATIONS

9.1 Endpoints

9.1.1 Primary Endpoint

Overall response rate will be evaluated using both RECIST and iRECIST criteria. Patients will have repeat imaging every 6 weeks to assess response.

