APPENDIX 2: DESCRIPTION OF THE IRECIST PROCESS FOR ASSESSMENT OF DISEASE PROGRESSION

Assessment at Screening and Prior to RECIST 1.1 Progression

Until radiographic progression based on RECIST 1.1, there is no distinct iRECIST assessment.

Assessment and Decision at RECIST 1.1 Progression

In participants who show evidence of radiological PD by RECIST 1.1 the Investigator will decide whether to continue a participant on study treatment until repeat imaging is obtained (using iRECIST for participant management (see Table 1 and Figure 1). This decision by the Investigator should be based on the participant's overall clinical condition.

Clinical stability is defined as the following:

- Absence of symptoms and signs indicating clinically significant progression of disease
- No decline in ECOG performance status
- No requirements for intensified management, including increased analgesia, radiation, or other palliative care

Any participant deemed clinically unstable should be discontinued from study treatment at site-assessed first radiologic evidence of PD, and is not required to have repeat tumor imaging for confirmation of PD by iRECIST.

If the Investigator decides to continue treatment, the participant may continue to receive study treatment and the tumor assessment should be repeated 4 to 8 weeks later to confirm PD by iRECIST, per Investigator assessment. I

Tumor flare may manifest as any factor causing radiographic progression per RECIST 1.1, including:

- Increase in the sum of diameters of target lesion(s) identified at baseline to $\geq 20\%$ and ≥ 5 mm from nadir
 - Please note: the iRECIST publication uses the terminology “sum of measurements”, but “sum of diameters” will be used in this protocol, consistent with the original RECIST 1.1 terminology.
- Unequivocal progression of non-target lesion(s) identified at baseline
- Development of new lesion(s)

iRECIST defines new response categories, including iUPD (unconfirmed progressive disease) and iCPD (confirmed progressive disease). For purposes of iRECIST assessment, the first visit showing progression according to RECIST 1.1 will be assigned a visit (overall) response of iUPD, regardless of which factors caused the progression.

At this visit, target and non-target lesions identified at baseline by RECIST 1.1 will be assessed as usual.

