New lesions will be classified as measurable or non-measurable, using the same size thresholds and rules as for baseline lesion assessment in RECIST 1.1. From measurable new lesions, up to 5 lesions total (up to 2 per organ), may be selected as New Lesions – Target. The sum of diameters of these lesions will be calculated, and kept distinct from the sum of diameters for target lesions at baseline. All other new lesions will be followed qualitatively as New Lesions – Non-target.

Assessment at the Confirmatory Imaging

On the confirmatory imaging, the participant will be classified as progression confirmed (with an overall response of iCPD), or as showing persistent unconfirmed progression (with an overall response of iUPD), or as showing disease stability or response (iSD/iPR/iCR).

Confirmation of Progression

Progression is considered confirmed, and the overall response will be iCPD, if ANY of the following occurs:

- Any of the factors that were the basis for the initial iUPD show worsening
 - For target lesions, worsening is a further increase in the sum of diameters of ≥ 5 mm, compared to any prior iUPD time point
 - For non-target lesions, worsening is any significant growth in lesions overall, compared to a prior iUPD time point; this does not have to meet the “unequivocal” standard of RECIST 1.1
 - For new lesions, worsening is any of these:
 - An increase in the new lesion sum of diameters by ≥ 5 mm from a prior iUPD time point
 - Visible growth of new non-target lesions
 - The appearance of additional new lesions
- Any new factor appears that would have triggered PD by RECIST 1.1

Persistent iUPD

Progression is considered not confirmed, and the overall response remains iUPD, if:

- None of the progression-confirming factors identified above occurs AND
- The target lesion sum of diameters (initial target lesions) remains above the initial PD threshold (by RECIST 1.1)

Additional imaging for confirmation should be scheduled 4 to 8 weeks from the scan on which iUPD is seen. This may correspond to the next visit in the original visit schedule. The

assessment of the subsequent confirmation scan proceeds in an identical manner, with possible outcomes of iCPD, iUPD, and iSD/iPR/iCR.

Resolution of iUPD

Progression is considered not confirmed, and the overall response becomes iSD/iPR/iCR, if:

- None of the progression-confirming factors identified above occurs, AND

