- The target lesion sum of diameters (initial target lesions) is not above the initial PD threshold.

The response is classified as iSD or iPR (depending on the sum of diameters of the target lesions), or iCR if all lesions resolve.

In this case, the initial iUPD is considered to be pseudo-progression, and the level of suspicion for progression is “reset”. This means that the next visit that shows radiographic progression, whenever it occurs, is again classified as iUPD by iRECIST, and the confirmation process is repeated before a response of iCPD can be assigned.

Management Following the Confirmatory Imaging

If repeat imaging does not confirm PD per iRECIST, as assessed by the Investigator, and the participant continues to be clinically stable, study treatment may continue and follow the regular imaging schedule. If PD is confirmed, participants will be discontinued from study treatment.

NOTE: If a participant has confirmed radiographic progression (iCPD) as defined above, but the participant is achieving a clinically meaningful benefit, an exception to continue study treatment may be considered. In this case, if study treatment is continued, tumor imaging should continue to be performed following the intervals as outlined above.

Detection of Progression at Visits After Pseudo-progression Resolves

After resolution of pseudo-progression (ie, achievement of iSD/iPR/iCR), iUPD is indicated by any of the following events:

- Target lesions
 - Sum of diameters reaches the PD threshold ($\geq 20\%$ and ≥ 5 mm increase from nadir) either for the first time, or after resolution of previous pseudo-progression. The nadir is always the smallest sum of diameters seen during the entire trial, either before or after an instance of pseudo-progression.
- Non-target lesions
 - If non-target lesions have never shown unequivocal progression, their doing so for the first time results in iUPD.

- If non-target lesions had shown previous unequivocal progression, and this progression has not resolved, iUPD results from any significant further growth of non-target lesions, taken as a whole.
- New lesions
 - New lesions appear for the first time
 - Additional new lesions appear
 - Previously identified new target lesions show an increase of ≥ 5 mm in the new lesion sum of diameters, from the nadir value of that sum
 - Previously identified non-target lesions show any significant growth

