If any of the events above occur, the overall response for that visit is iUPD, and the iUPD evaluation process (see Assessment at the Confirmatory Imaging above) is repeated. Progression must be confirmed before iCPD can occur.

The decision process is identical to the iUPD confirmation process for the initial PD, except in one respect. If new lesions occurred at a prior instance of iUPD, and at the confirmatory scan the burden of new lesions has increased from its smallest value (for new target lesions, their sum of diameters is ≥ 5 mm increased from its nadir), then iUPD cannot resolve to iSD or iPR. It will remain iUPD until either a decrease in the new lesion burden allows resolution to iSD or iPR, or until a confirmatory factor causes iCPD.

Additional details about iRECIST are provided in the iRECIST publication.[46]

**APPENDIX 3: EASTERN COOPERATIVE ONCOLOGY GROUP (ECOG)
PERFORMANCE STATUS SCALE ASSESSMENT**

ECOG Performance Status Scale	
Grade	Descriptions
0	Normal activity. Fully active, able to carry on all pre-disease performance without restriction.
1	Symptoms, but ambulatory. Restricted in physically strenuous activity, but ambulatory and able to carry out work of a light or sedentary nature (e.g., light housework, office work).
2	In bed <50% of the time. Ambulatory and capable of all self-care, but unable to carry out any work activities. Up and about more than 50% of waking hr.
3	In bed >50% of the time. Capable of only limited self-care, confined to bed or chair more than 50% of waking hr.
4	100% bedridden. Completely disabled. Cannot carry on any self-care. Totally confined to bed or chair.
5	Dead.

**APPENDIX 4: COMMON TERMINOLOGY CRITERIA FOR ADVERSE EVENTS V5.0
(CTCAE)**

The descriptions and grading scales found in the revised NCI Common Terminology Criteria for Adverse Events (CTCAE) version 5.0 will be utilized for adverse event reporting. (<http://ctep.cancer.gov/reporting/ctc.html>)

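### After a first iUPD, Appendix 2 can class a patient as iSD or iPR while the new lesion or non-target progression that caused it is still present but not worsening; this can only raise the iRECIST rates

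*Combined protocol and SAP*

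**What the plan says.** Appendix 2 allows three causes of a first iUPD: growth of the target sum, a new lesion, or "Unequivocal progression of non-target lesion(s) identified at baseline". The visit is iUPD whichever of these applies.

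The repeat scan has three outcomes.

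- **iCPD**, if the original cause worsens or a new factor appears that would itself be RECIST 1.1 progression.
- **Persistent iUPD**, under two joint conditions. The first is worded "None of the progression-confirming factors identified above occurs AND". It is linked to a second, which concerns size only: "The target lesion sum of diameters (initial target lesions) remains above the initial PD threshold (by RECIST 1.1".
- **Resolution**, under the same first condition together with "The target lesion sum of diameters (initial target lesions) is not above the initial PD threshold". The visit is then iSD or iPR according to the target sum. Only iCR needs every lesion to have gone. The text adds: "In this case, the initial iUPD is considered to be pseudo-progression". Suspicion of progression is reset, so the next progression again needs confirming.

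For episodes after a resolution, Appendix 2 adds one exception. If the new-lesion burden has risen from its smallest value, the visit cannot resolve: "It will remain iUPD until either a decrease in the new lesion burden allows resolution to iSD or iPR".

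On the endpoints, Section 9.1.1 states: "Overall response rate will be evaluated using both RECIST and iRECIST criteria". Section 6.1.1 states: "Clinical benefit rate (stable disease + responses) will be assessed using the same criteria as response rate and on the same schedule". Sections 1.5.4 and 2.1 and Appendix 1 make RECIST 1.1 the main measure of response, with iRECIST assessed as well.

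**The concern.** Three kinds of finding can open an iUPD, but absent worsening only one of them, the target sum, decides whether it closes. A patient whose targets never progressed, and who became iUPD because of a new metastasis, meets the closing condition from the outset. If that metastasis is simply still there at the repeat scan, the patient is recorded as having had pseudo-progression.

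This sits badly with the reason for iRECIST given in Section 1.5.5, which is a temporary flare followed by response. An unchanged new lesion shows neither a flare that has passed nor a response. It also sits badly with the later-episode exception, where a fall in new-lesion burden is what permits resolution. That safeguard is not given to the first episode.

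At stake are the iRECIST response rate and the iRECIST clinical benefit rate. Patients can move only from iUPD, which counts in neither rate, to iSD or iPR, so the effect has one direction.

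**Working it through.** The plan gives no figure on this point, so the check is of the rule itself, followed by simple arithmetic.

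**1. The rule as written.** The table is the same for all three causes of the first iUPD.

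| Confirming factor at repeat scan | Initial target sum | Label |
|---|---|---|
| Yes | Either | iCPD |
| No | Above PD threshold | iUPD |
| No | Not above PD threshold | iSD or iPR (iCR if all lesions resolve) |

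Persistence of a lesion is not a confirming factor. Measured new lesions need a rise of at least 5 mm in their sum; other new lesions need visible growth; a further new lesion also confirms. Non-target disease needs significant growth.

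Suppose the target sum had not crossed the threshold at the first iUPD. The middle row is then out of reach, because a later crossing would be a new progression factor and so iCPD. Only iCPD or resolution remains.

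**2. A case ending in iPR (hypothetical measurements).**

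- Baseline: target sum 100 mm.
- Week 6: targets 65 mm (−35%), plus a new 12 mm lesion followed as a new target lesion. This is RECIST 1.1 progression and iUPD. PD threshold = 1.2 × 65 = 78 mm; that rise of 13 mm also passes the 5 mm minimum.
- Week 12: targets 64 mm, new lesion 16 mm. Rise in new-lesion sum = 16 − 12 = 4 mm, below 5 mm, and no further lesion. 64 mm is not above 78 mm, so the iUPD resolves. Target change = (64 − 100)/100 = −36%, so the label is iPR.

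The label would be the same had the new lesion stayed at 12 mm. Section 6.3.5 asks for response to be confirmed at least 4 weeks later, so this single scan is not yet a confirmed response. A new lesion that remains at 16 mm would not prevent confirmation.

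**3. A case ending in iSD.** Targets are 100 mm at every scan, and a new 12 mm lesion appears at week 6 and does not change. Threshold = 1.2 × 100 = 120 mm. 100 mm is not above it, and the target change is 0%, so week 12 is iSD.

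Under RECIST 1.1 both patients progressed at week 6, and neither is a responder.

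**4. Effect on the rates.** Section 9.4.2 uses best response over all evaluable patients. With 34 evaluable, one patient is 1/34 = 0.0294, or 2.9 points. Whether that is added depends on what came before the iUPD.

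| Before the iUPD | After relabelling | iRECIST ORR | iRECIST clinical benefit rate |
|---|---|---|---|
| No SD or response | iSD | no change | +2.9 points |
| No SD or response | iPR, confirmed | +2.9 points | +2.9 points |
| SD | iPR, confirmed | +2.9 points | no change |
| Confirmed PR | iSD or iPR | no change | no change |

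The documents give no frequency. If 1 to 3 such patients are assumed, the addition is 1/34 to 3/34, or 2.9 to 8.8 points.

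**The case against.** The strongest reply is that the rule is narrower than it first looks and appears deliberate.

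- **Worsening is covered.** A reader might infer that resolution rests on the target sum alone, so that growing disease is also relabelled. The documents do not support that. The no-worsening condition is joined by AND, so growing or multiplying lesions give iCPD. What remains is disease that is present and not worsening by the appendix's own limits.
- **The text is not plainly self-contradictory.** For visits after a resolution, Appendix 2 expressly provides for non-target progression that is still unresolved and watches it for further growth. It states that later episodes differ from the first in one respect, and that exception concerns increased burden, not an unchanged lesion. Whether the rule departs from the cited iRECIST publication cannot be judged from these documents. This stands: the point is a poor fit with the stated purpose, not a proven error of transcription.
- **The primary decision is not reached.** Because Section 9.1.1 names both criteria, a reader might carry the effect into the two-stage test. If relabelling lifted a 10% rate to 12.9%, the chance of passing (at least 2 of 13, then at least 6 of 34) would go from 0.096 to 0.22. But Section 9.4.1 never applies that rule to an iRECIST count, and Sections 1.5.4 and 2.1 and Appendix 1 put RECIST 1.1 first. Those probabilities describe a test that the plan does not specify.
- **Not every case adds to a rate.** This is right, as the second table shows.
- **Changing the label would change management.** Table 1 ties treatment and repeat imaging at 4 to 8 weeks to these labels. This also stands, and it limits the fix.

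**Conclusion.** The point holds in a limited form. In a first episode caused by a new lesion or non-target progression, with the target sum not above the PD threshold, disease that is still visible but not worsening is classified iSD or iPR and called pseudo-progression. This can only raise the iRECIST response rate and clinical benefit rate, by up to 2.9 points per patient without an earlier qualifying response, assuming 34 evaluable patients. The frequency is unknown. An iPR case also needs at least 30% target shrinkage alongside a persisting lesion, and the patient must remain under imaging.

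The RECIST 1.1 response rate and the two-stage decision are unaffected. The conclusion follows from the wording of Appendix 2 and needs no outside source.

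**What to change.** Add a derivation rule to Section 9.4.2. For the iRECIST ORR and clinical benefit rate, a visit after iUPD does not count as iSD or iPR while the new lesion or non-target progression that triggered the iUPD is still present and has not regressed. State in advance what counts as regression, since Appendix 2 gives no limit for it. Apply the existing confirmation requirement of Section 6.3.5 to iRECIST responses.

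The cost is a few sentences and slightly lower iRECIST rates. Because the rule governs only how the rates are derived, it adds no patients and no scans. Appendix 2 already has new lesions measured or followed at each assessment.

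For treatment and imaging, ask the sponsor to reconcile the persistence, resolution and later-episode rules of Appendix 2 with Table 1. This review does not say which label should govern management.

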APPENDIX 5: CONTRACEPTIVE GUIDANCE AND PREGNANCY TESTING

Woman of Childbearing Potential (WOCBP)

A woman is considered fertile following menarche and until becoming post-menopausal unless permanently sterile (see below)

Women in the following categories are not considered WOCBP:

- Premenarchal
- Premenopausal female with 1 of the following:
 - Documented hysterectomy
 - Documented bilateral salpingectomy
 - Documented bilateral oophorectomy

Note: Documentation can come from the site personnel's review of the participant's medical records, medical examination, or medical history interview.

- Postmenopausal female
 - A postmenopausal state is defined as no menses for 12 months without an alternative medical cause.
 - A high follicle stimulating hormone (FSH) level in the postmenopausal range may be used to confirm a postmenopausal state in women not using hormonal contraception or hormonal replacement therapy (HRT). However, in the absence of 12 months of amenorrhea, confirmation with two FSH measurements in the postmenopausal range is required.
- Females on HRT and whose menopausal status is in doubt will be required to use one of the non-hormonal highly effective contraception methods if they wish to continue their HRT during the study. Otherwise, they must discontinue HRT to allow confirmation of postmenopausal status before study enrollment.

Contraception Requirements

Male Participants:

Male participants with female partners of childbearing potential are eligible to participate if they agree to one of the following during the protocol defined time frame:

- Be abstinent from penile-vaginal intercourse as their usual and preferred lifestyle (abstinent on a long term and persistent basis) and agree to remain abstinent
- Use a male condom plus partner use of a contraceptive method with a failure rate of <1% per year when having penile-vaginal intercourse with a woman of childbearing potential who is not currently pregnant.
- Note: Men with a pregnant or breastfeeding partner must agree to remain abstinent from penile-vaginal intercourse or use a male condom during each episode of penile penetration.

Female participants:

Female Participants:

Female participants of childbearing potential are eligible to participate if they agree to use a highly effective method of contraception consistently and correctly as described in Table 8 during the protocol-defined time frame.

Table 8 : Highly Effective Contraception Methods

Highly Effective Contraceptive Methods That Are User Dependent ^a Failure rate of <1% per year when used consistently and correctly.	

 • Combined (estrogen- and progestogen- containing) hormonal contraception ^{b, c} 
 • Oral • Intravaginal • Transdermal • Injectable 	
Progestogen-only hormonal contraception ^{b, c} 
 • Oral • Injectable 	
Highly Effective Methods That Have Low User Dependency Failure rate of <1% per year when used consistently and correctly.	

 • Progestogen- only contraceptive implant ^{b, c} • Intrauterine hormone-releasing system (IUS) ^b • Intrauterine device (IUD) • Bilateral tubal occlusion 	
Vasectomized partner A vasectomized partner is a highly effective contraception method provided that the partner is the sole male sexual partner of the WOCBP and the absence of sperm has been confirmed. If not, an additional highly effective method of contraception should be used.	
Sexual abstinence Sexual abstinence is considered a highly effective method only if defined as refraining from heterosexual intercourse during the entire period of risk associated with the study treatment. The reliability of sexual abstinence needs to be evaluated in relation to the duration of the study and the preferred and usual lifestyle of the participant.)	
Notes: Use should be consistent with local regulations regarding the use of contraceptive methods for participants of clinical studies.	
a) Typical use failure rates are lower than perfect-use failure rates (i.e. when used consistently and correctly). b) If hormonal contraception efficacy is potentially decreased due to interaction with study treatment, condoms must be used in addition to the hormonal contraception during the treatment period and for at least 3 months after the last dose of study treatment.	

c) If locally required, in accordance with Clinical Trial Facilitation Group (CTFG) guidelines, acceptable hormonal contraceptives are limited to those which inhibit ovulation.

Pregnancy Testing

WOCBP should only be included after a negative highly sensitive urine or serum pregnancy test.

Following initiation of treatment, pregnancy testing will be performed whenever an expected menstrual cycle is missed or when pregnancy is otherwise suspected; at the time points specified in the Schedule of Activities, and as required locally.

Pregnancy testing will be performed whenever an expected menstrual cycle is missed or when pregnancy is otherwise suspected.

PROTOCOL NUMBER: OSU-19132

CONFIDENTIAL
